### **Power**

To our knowledge, there are no intervention studies that specifically examined the efficacy of physical therapy on balance in people with PD with STN-DBS. Given that this is a pilot study, the authors chose an effect size that would be meaningful and required to support moving forward with a larger trial. As such, with a medium effect size of 0.25 (Cohen's  $f$ ) and an alpha level of 0.05, 14 participants per group will provide 82% power to detect significant differences between or within groups for the primary preliminary efficacy outcome (i.e., BESTest). Factoring in a potential for 20% dropout attrition rate based on prior studies, we plan to recruit 17 participants per group. This pilot study is not powered to detect significant differences in the number of adverse events between groups.

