**Official Title: Physical Therapy and Deep Brain Stimulation in Parkinson Disease**

**NCT Number: NCT03181282**

**Document Date: May 11, 2017**

## **I. Specific Aims**

The purpose of this study is to examine the safety, feasibility, and preliminary efficacy of PT in people with PD with STN-DBS. We expect that participants with STN-DBS in the PT group will not report more adverse effects than those in the control group. Furthermore, we hypothesize that those in the PT group will complete at least 80% of prescribed PT sessions. We also expect that those in the PT group will demonstrate improvements in balance and gait while those in the control group will demonstrate no change or a decline in balance and gait.

Specific Aim 1: To determine the safety of an 8-week PT intervention in people with STN-DBS. The primary variable of interest for safety is the number of adverse events (e.g. falls, orthopedic injuries).

Hypothesis 1: We hypothesize that participants with STN-DBS plus PT will not report more adverse effects than those with STN-DBS only.

Specific Aim 2: To determine the feasibility of an 8-week PT intervention in people with STN-DBS. The primary variable of interest for feasibility is adherence to the PT intervention, measured as a percentage of PT sessions completed.

Hypothesis 2: We hypothesize that participants with STN-DBS will complete at least 80% of prescribed PT sessions.

Specific Aim 3A: To evaluate the preliminary efficacy of PT on balance in people with STN-DBS. The primary variable of interest is the Balance Evaluation Systems Test (BESTest) total score.

Hypothesis 3A: We hypothesize that participants with STN-DBS plus PT will demonstrate improvements in balance while those with STN-DBS only will demonstrate no change or a decline in balance.

Specific Aim 3B: To determine the preliminary efficacy of PT on gait in people with STN-DBS. The primary variables of interest is preferred-pace gait velocity.

Hypothesis 3B: We hypothesize that participants with STN-DBS plus PT will demonstrate improvements in preferred-pace gait velocity while those with STN-DBS only will demonstrate no change or a decline in gait.

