### **Follow-Up Testing**

The 8-week and 12-week follow up visits will occur as soon as possible after the intervention is completed. The same protocol completed at baseline will be followed for this assessment. Again participants will be tested in the OFF stimulation / OFF medication and ON stimulation / ON medication conditions on two separate days. The OFF stimulation / OFF medication visit will last approximately 3 hours and the ON stimulation / ON medication visit will last approximately 2 hours.

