### **Statistical Analysis Plan**

The total number of adverse events will be reported for each group allowing for qualitative comparisons.

Adherence will be reported for both attendance of PT and control sessions and will be expressed as percent of sessions completed.

Balance and gait data will be analyzed using mixed models with repeated measures or appropriate non-parametric test as appropriate to test for main effects of group (PT, control) and time (baseline, 8-weeks) and group\*time interactions ( $\alpha \leq 0.05$ ).

If there are baseline differences in demographic variables (e.g. age, gender, years since PD diagnosis, years since DBS), we will use these variables as covariates in the analyses.

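### The 82% power for f = 0.25 does not extend to a medium between-arm benefit: for group-by-time, f = 0.25 is a 1.0 SD difference in change, and 0.5 SD has about 25–38% power

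*Combined protocol and SAP*

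**What the plan says.** The Power section of the combined protocol and SAP assumes Cohen's f "with a medium effect size of 0.25" and "an alpha level of 0.05". It concludes that "14 participants per group will provide 82% power to detect significant differences between or within groups" for the "primary preliminary efficacy outcome (i.e., BESTest"). The size of the effect is justified in one sentence: "the authors chose an effect size that would be meaningful and required to support moving forward with a larger trial".

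The Statistical Analysis Plan section tests "main effects of group (PT, control) and time (baseline, 8-weeks"), together with the group-by-time interaction. Hypothesis 3A in the Specific Aims expects that "participants with STN-DBS plus PT will demonstrate improvements in balance while those with STN-DBS only will demonstrate no change or a decline in balance". That is a statement about a between-arm difference in change, so group-by-time is the test that answers it.

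Follow-Up Testing also provides for a third assessment ("The 8-week and 12-week follow up visits"), but the 12-week visit is not in the analysis model. The documents give no within-person correlation, no BESTest standard deviation, no difference in points and no sidedness.

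**The concern.** For a plain comparison of two means, f = d/2, so f = 0.25 is 0.5 SD. Many readers will carry that equivalence over to this trial and conclude that it has 82% power for a half-SD advantage of PT over control. In a repeated-measures model the same f does not mean the same thing. When the effect is an interaction, f = 0.25 is a difference in change twice that size.

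The stated power covers between-group and within-group differences in one phrase, although a single f gives very different power for the two. What is at stake is how a null result is read. If the trial is believed to have 82% power for a medium benefit, a non-significant BESTest result will look like evidence against such a benefit, when in fact most trials of this size would miss it.

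**Working it through.** **Inputs.** From Power: f = 0.25, alpha 0.05, 14 per group (N = 28). From the Statistical Analysis Plan: two groups and m = 2 time points. From Specific Aims: the pattern in Hypothesis 3A. Assumptions: a two-sided test, because sidedness is not stated; and a within-person correlation ρ of 0.5 to 0.7, because none is given. Effects are in units of the between-person SD of the BESTest.

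**Formulas (noncentral F).**
- Time or group-by-time: λ = f²·N·m/(1 − ρ), with df (m − 1) and (N − 2)(m − 1).
- Group main effect: λ = f²·N·m/(1 + (m − 1)ρ), with df 1 and N − 2.

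**Step 1: reproduce the 82%.** With m = 2, f²·N·m = 0.0625 × 28 × 2 = 3.5.
- Group-by-time, λ = 3.5/(1 − ρ): ρ = 0.5 gives λ = 7.00 and power 72.1%; ρ = 0.61 gives 8.97 and 82.2%; ρ = 0.7 gives 11.67 and 90.8%.
- Group main effect, λ = 3.5/(1 + ρ): 2.33, 2.17 and 2.06 at the same correlations, with power 31.3%, 29.5% and 28.2%.
- Three time points, ρ = 0.5: λ = 0.0625 × 28 × 3/0.5 = 10.5 on 2 and 52 df, power 81.2%.
- One-sided 5% test, two time points, ρ = 0.5: λ = 7.00, power 82.4%. Nothing in the plan indicates a one-sided test.

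So a figure near 82% can be recovered for a within-person or interaction effect in more than one way. None of the group main effect calculations comes near it.

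**Step 2: turn f into a difference.** Let control change by c and PT by p between baseline and 8 weeks, with equal baselines, and let D = p − c. Removing the group and time effects from the four cell means leaves residuals of ±D/4, so the interaction f is D/4.
- f = 0.25 gives D = 4 × 0.25 = 1.0 SD.
- D = 0.5 SD gives f = 0.5/4 = 0.125.

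This conversion does not depend on ρ. D equals PT's own gain only if controls do not change. PT +0.5 SD with control −0.5 SD also gives D = 1.0 SD and f = 0.25.

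**Step 3: power for D = 0.5 SD.** f²·N·m = 0.015625 × 56 = 0.875, so λ = 0.875/(1 − ρ).

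| ρ (assumed) | λ for D = 1.0 SD | Power | λ for D = 0.5 SD | Power |
|---|---|---|---|---|
| 0.5 | 7.00 | 72% | 1.75 | 25% |
| 0.61 | 8.97 | 82% | 2.24 | 30% |
| 0.7 | 11.67 | 91% | 2.92 | 38% |

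Simulated t tests on change scores (20,000 trials each) agree: at ρ = 0.614, 82.4% for 1.0 SD and 30.6% for 0.5 SD; at ρ = 0.5, 72.2% and 24.7%.

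**Step 4: the other routes to 82%.** With three time points and ρ = 0.5, f = 0.125 has 27% power, and a 0.5 SD gain held at both follow-ups (f = 0.118) has 24.5%. In that model f = 0.25 corresponds to 1.06–1.22 SD, depending on the course after week 8. Under the one-sided reading, D = 0.5 SD (λ = 1.75) has 36%. A higher correlation does not reconcile the figures: at ρ = 0.8, 0.5 SD has 52%, but f = 0.25 would then have 98%, not 82%.

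**Step 5: what a null result would exclude.** The expected standard error of D is √(4(1 − ρ)/14) SD: 0.378, 0.334 and 0.293 at ρ = 0.5, 0.61 and 0.7. Multiplied by t(26) = 2.056, the expected 95% half-width is 0.78, 0.69 and 0.60 SD. With a half-width above 0.5 SD, a non-significant estimate anywhere from zero upwards leaves 0.5 SD inside its interval.

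**The case against.** The plan has a fair defence. The value 0.25 is medium on the f scale that it cites, so the label is not a slip. Nowhere does the plan say 0.5 SD or claim 82% power for it. A reader might infer that the arithmetic is wrong and that the true power is 30% rather than 82%. The documents do not support that: the 82% can be reproduced for f = 0.25, and the 30% belongs to a different effect at a correlation that the plan does not state.

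A reader might also infer that PT patients themselves must improve by 1.0 SD. Hypothesis 3A allows controls to worsen, and then a smaller PT gain is enough. With PT +0.5 and control −0.2 SD, for example, power at ρ = 0.61 is about 52%.

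Third, a reader might infer that a p-value above 0.05 would stop the programme, or that an inflated significant estimate would feed the next sample-size calculation. No section sets a significance rule for progression. The Power section ties it to an effect size, and the Background ties future studies to safety and feasibility. Those harms are possible but are not written into the plan.

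What remains is that the power statement covers between-group differences without qualification. On neither reading, interaction or group main effect, does the design deliver 82% for a medium between-arm benefit.

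**Conclusion.** The concern holds as a fault in how the detectable effect is stated. It should be fixed, but it is not an arithmetic error and does not undermine the pilot. Under the two-time-point group-by-time test, the design has 72–91% power for a 1.0 SD between-arm difference in 8-week change, and about 25–38% for 0.5 SD. As a group main effect, f = 0.25 has about 28–31%.

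The conversion of f = 0.25 to 1.0 SD is exact for the two-by-two model. The power figures rest on a two-sided 5% test, 14 completers per arm and an assumed correlation of 0.5 to 0.7; the other settings that reproduce roughly 82% put a 0.5 SD difference at about 24–36%. In points the size is unknown. If the BESTest SD were 10 to 20 points (an assumption), the trial would be sized for 10 to 20 points, and a 0.5 SD benefit would be 5 to 10.

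**What to change.** Amend the Power section as follows:

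1. Say that the power applies to the group-by-time test at baseline and 8 weeks, and state the assumed within-person correlation. If the 82% was calculated with three time points, say so and align it with the analysis model.
2. Replace the description of the effect with: *f = 0.25, i.e. a between-arm difference in 8-week BESTest change of 1.0 SD*, and give its value in points under a stated SD.
3. Remove the general claim of 82% for differences between and within groups.
4. Add the power for a 0.5 SD difference in change: about 25–38% for correlations of 0.5–0.7.
5. State that a non-significant result does not exclude a 0.5 SD benefit, and that efficacy will be reported as the between-arm difference in change with its 95% CI.

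The change is to wording only, with no change in enrolment. The cost is a less favourable power statement.

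### The single 82% power figure cannot hold for both between-group and within-group effects: where the group-by-time test reaches 82%, the planned main effect of group has about 30%

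*Combined protocol and SAP*

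**What the plan says.** The Power section takes an effect "with a medium effect size of 0.25" on Cohen's f scale and "an alpha level of 0.05", and concludes that "14 participants per group will provide 82% power to detect significant differences between or within groups for the primary preliminary efficacy outcome", the BESTest. It then allows for losses: "Factoring in a potential for 20% dropout attrition rate based on prior studies, we plan to recruit 17 participants per group".

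The Statistical Analysis Plan uses a repeated-measures model "to test for main effects of group (PT, control) and time (baseline, 8-weeks"), together with the group-by-time interaction. Hypothesis 3A in the Specific Aims is about differential change: the PT group "will demonstrate improvements in balance while those with STN-DBS only will demonstrate no change or a decline in balance".

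The Follow-Up Testing section adds a third assessment ("The 8-week and 12-week follow up visits will occur as soon as possible after the intervention is completed"), but the 12-week visit is not in the analysis model. The documents give no correlation between repeated BESTest scores.

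**The concern.** One power figure is attached to two kinds of effect that respond in opposite ways to the within-person correlation. A higher correlation makes change scores more precise, so power for time and group-by-time rises. It also makes each person's average over visits less precise, so power for the main effect of group falls. A single f, a single sample size and a single 82% are therefore unlikely to fit both.

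This paragraph is the only sample-size justification in the documents, and it ties the chosen effect to the decision to move on to a larger trial. Read as written, a non-significant main effect of group on the BESTest would seem to come from a test with 82% power. For the group-by-time test, the reader cannot tell what the 82% depends on.

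**Working it through.** **Inputs from the documents.** f = 0.25, alpha 0.05, 14 per group (N = 28) and stated power 82% (Power); tests of group, time and group-by-time at baseline and 8 weeks (Statistical Analysis Plan); 1:1 allocation (Randomization Method).

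**Assumptions.** The correlation ρ between repeated measurements is not given, so a range is shown. f is scaled to the SD of a single measurement and applied to each effect in turn, because the text gives only one value.

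**Formulas.** Noncentral F with m measurements:

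- Time and group-by-time: λ = f²·N·m / (1 − ρ), with df (m − 1) and (N − 2)(m − 1).
- Main effect of group: λ = f²·N·m / (1 + (m − 1)ρ), with df 1 and N − 2.

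**Reproducing the 82%.** With m = 2, f²·N·m = 0.0625 × 28 × 2 = 3.5. At ρ = 0.608 the group-by-time λ is 3.5/0.392 = 8.93 and power is 82.0%. With m = 3 the product is 5.25; at ρ = 0.5, λ = 10.5 and power is 81.2%, and 82% is reached at ρ of about 0.51. So the figure can be reproduced for the interaction, under assumptions the documents do not state.

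**Both effects side by side, m = 2, N = 28:**

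| ρ | λ, group-by-time | Power | λ, group | Power |
|---|---|---|---|---|
| 0 | 3.50 | 44% | 3.50 | 44% |
| 0.3 | 5.00 | 58% | 2.69 | 35% |
| 0.5 | 7.00 | 72% | 2.33 | 31% |
| 0.608 | 8.93 | 82% | 2.18 | 30% |
| 0.7 | 11.67 | 91% | 2.06 | 28% |
| 0.8 | 17.50 | 98% | 1.94 | 27% |

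The two powers agree only at ρ = 0, at 43.7%. From there one rises and the other falls, towards about 25% for the main effect of group as ρ approaches 1. No non-negative ρ gives 82% for both. With m = 3 the main effect of group has 60% at ρ = 0 and 35% at 0.5.

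A simulation (40,000 trials per setting, m = 2, 14 per group) agrees. Group-by-time and group powers were 43.5% and 44.2% at ρ = 0, 72.0% and 31.2% at 0.5, and 82.0% and 29.7% at 0.608.

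**Size of the gap.** For 82% on the two-time-point main effect of group at f = 0.25, the trial would need 35 per group at ρ = 0, 51 at 0.5 and 55 at 0.608. With 14 per group, f would have to be 0.40, 0.49 and 0.51 respectively.

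**What f = 0.25 means for the interaction.** On this scaling each of the four cell means departs from additivity by 0.25 SD, so the between-group difference in change is 4 × 0.25 = 1.0 SD. Check at ρ = 0.5: the variance of a change score is 2(1 − 0.5) = 1, so λ = 1.0²/(2/14) = 7.0, as in the table.

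**Attrition (minor).** 17 × 0.8 = 13.6, below the 14 on which the power rests; 14/0.8 = 17.5. With 13 completers per group, group-by-time power is 69% at ρ = 0.5, 78% at 0.6 and 88% at 0.7.

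**The case against.** The strongest reply is that the Power section never mentions a main effect of group. Its wording may be a loose way of describing the within-between interaction, which is what Hypothesis 3A calls for. On that reading 82% needs only an unremarkable correlation, and the defect is incomplete reporting rather than a wrong number. No efficacy hypothesis turns on the main effect of group, which in this design averages in the pre-treatment value, and the study is a pilot with preliminary efficacy aims.

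Much of this stands. The 82% may be correct for the interaction, and the low power of the main effect matters chiefly because the sentence promises otherwise. But the Statistical Analysis Plan does list that main effect, so a reader will naturally take the claim to cover it. The interaction-only reading still needs ρ of about 0.61. If the figure came from three measurements at ρ near 0.5, which is possible but unconfirmed, it does not match the two-time-point model, which has 72% at ρ = 0.5.

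Two technical points are also fair. First, the scaling of f is an assumption. If f already absorbed the correlation (λ of about f² times the error df), the interaction would have about 23% power whatever the correlation. That cannot produce 82%, so the scaling used here is the more plausible one. Second, each visit is tested in two stimulation and medication conditions. If all six measurements were pooled, the main effect of group would have 88% at ρ = 0 and 83% at ρ = 0.03. Those correlations are unrealistic, the group-by-time power there is only 68% to 70%, and this is not the model described.

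The attrition shortfall is small, as the objection would say: losing 3 of 17 leaves exactly 14, and a mixed model can use partial data.

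**Conclusion.** The concern holds. At f = 0.25, alpha 0.05 and 14 per group, the claimed 82% is not available for the planned main effect of group. That effect has 25% to 44% with two time points and at most 60% with three, over all non-negative correlations. For the group-by-time test the 82% is attainable but conditional on an unstated correlation of about 0.61; across 0.3 to 0.7 the power is 58% to 91%. These results rest on assumed correlations, on f being scaled to the SD of a single measurement, and on the same f applying to each effect. The paragraph should be corrected, but the design itself is not invalidated, since the hypothesis of interest is tested by the interaction.

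**What to change.** Reword the Power paragraph as follows.

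- Remove the wording that extends the figure to between-group and within-group differences alike.
- State power for the group-by-time contrast on the BESTest at baseline and 8 weeks, naming the assumed correlation and giving the range: 58% at 0.3, 72% at 0.5, 81% at 0.6 and 91% at 0.7.
- If the 82% came from three time points, say so and reconcile it with the two-time-point model in the Statistical Analysis Plan.
- Say that the main effect of group is not powered.
- Preferably, state how f is scaled and add that, on the scaling used here, f = 0.25 is a 1.0 SD between-group difference in change (for example, PT up 1.0 SD with control unchanged).
- Minor: describe the attrition allowance as about 18% (3/17 = 17.6%), or give the power with 13 completers per group.

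The cost is one rewritten paragraph, with no extra participants and no change to the analysis. The drawback is that the stated power becomes conditional on a correlation and may look less favourable.

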### **Randomization Method**

Participants will be randomly assigned (1:1 ratio) to either the PT intervention group or the control group in a consecutive fashion using an internet randomization scheme generator. A study team member will write the group assignment number on a piece of paper wrapped in tin foil. This will be placed in an opaque envelope and sealed. After participants complete both baseline assessment they will be allowed to open the envelope to determine their group assignment.

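### Recruiting 17 per group falls slightly short of the plan's own 20% dropout allowance: about 13.6 per group are expected to remain, not the 14 behind the stated power

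*Combined protocol and SAP*

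**What the plan says.** The Power section of the combined protocol and SAP gives a short sample size argument for the BESTest, the primary preliminary efficacy outcome. It assumes Cohen's f of 0.25 and "an alpha level of 0.05", and states that "14 participants per group will provide 82% power to detect significant differences between or within groups". The next sentence makes the allowance for attrition: "Factoring in a potential for 20% dropout attrition rate based on prior studies, we plan to recruit 17 participants per group". It gives no inflation formula and no rounding rule.

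Two other sections bear on the check. Randomization Method sets equal allocation, so the totals are 28 for the power and 34 for recruitment. The Statistical Analysis Plan section specifies a mixed model with group, time and their interaction, and lists two time points, baseline and 8 weeks. Follow-Up Testing also describes a 12-week visit. The plan states neither the within-person correlation nor the number of measurements behind the 82%.

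**The concern.** The recruitment figure is there to ensure that, after the expected losses, the number on which the power was calculated is still available. Three figures should therefore fit together: 14 per group needed, 20% lost, 17 per group recruited. Dropout is a fraction of those recruited, so the check is whether 80% of 17 reaches 14. It does not.

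What is at stake is modest. At the plan's own dropout rate, its own recruitment figure does not deliver the group size to which the 82% belongs. The section presents the study as a step towards a larger trial, so the sample size paragraph may be reused. If the allowance was made by multiplying by 1 + d, the shortfall from that method grows as the dropout rate d rises.

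**Working it through.** **Inputs from the Power section.** Required number n = 14 per group; dropout d = 0.20; recruited 17 per group; f = 0.25; alpha = 0.05. With 1:1 allocation the totals are 28 and 34.

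**1. Reproducing the stated 17.**
- n x (1 + d) = 14 x 1.20 = 16.8, rounded up to 17. This matches.
- n / (1 - d) = 14 / 0.80 = 17.5, rounded up to 18. This does not match. Rounded down, it would also give 17.

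**2. What 17 per group leaves.**
- Expected to remain: 17 x 0.80 = 13.6 per group, or 34 x 0.80 = 27.2 in total. The shortfall is 0.4 per group and 0.8 in total.
- Largest loss that still leaves 14: 3 of 17, and 3/17 = 17.6%, which is below the stated 20%. A fourth loss leaves 13.
- For comparison, 18 per group leaves 18 x 0.80 = 14.4.

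**3. Effect on power.** The power of the repeated-measures group-by-time F test was taken from the noncentral F distribution. With m measurements, correlation rho, k = 2 groups and N in total:

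- noncentrality = f² x N x m / (1 - rho)
- degrees of freedom: (m - 1)(k - 1) and (N - k)(m - 1)

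The plan gives neither rho nor the m used for its power. The values here are assumptions: rho = 0.5, with m = 3 (baseline, 8 and 12 weeks) or m = 2 (the time points in the Statistical Analysis Plan section). At N = 28 the noncentrality is 0.0625 x 28 x 3 / 0.5 = 10.5 for m = 3, and 0.0625 x 28 x 2 / 0.5 = 7.0 for m = 2. A third setting keeps m = 2 and chooses rho (about 0.61) so that N = 28 gives exactly 82%.

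| Setting | N = 28 (14 per arm) | N = 27.2 (expected) | N = 26 (13 per arm) |
|---|---|---|---|
| m = 3, rho = 0.5 | 81.2% | 79.9% | 77.8% |
| m = 2, rho = 0.5 | 72.1% | 70.8% | 68.7% |
| m = 2, rho about 0.61 | 82.0% | 80.8% | 78.9% |

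The first and third settings come close to or match the stated 82%. In all three, the expected loss is 1.2 to 1.3 points, and the loss if each arm ends with 13 is a little over 3 points. The value at N = 27.2 is an interpolation, since the number of participants must be whole.

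**The case against.** The strongest reply is that the gap is trivial. It is 0.4 of a person per arm, 13.6 rounds to 14, the 20% is a planning allowance and not a forecast, and this is a pilot. As a statement about size this stands. It does not make the figures agree: 17 keeps 14 only if losses stay at or below 17.6%, and a number meant to secure a minimum is normally rounded up at the recruitment step.

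A second reply is that a mixed model keeps a dropout's baseline record, so those who complete are not strictly the number analysed. This is true, but with only baseline and 8 weeks in the model, a participant with baseline alone adds little to the group-by-time contrast. The plan itself inflates for attrition, which treats 14 as the number left after dropout.

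Some stronger readings are tempting, and the documents do not support them:

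- **That the plan used the wrong inflation formula.** 14 x 1.20 fits, but so does 17.5 rounded down. No formula is given, so this stays an inference.
- **That about 3 points of power are lost.** That is the loss when each arm ends with 13. At the expected 13.6 per arm it is about 1.3 points.
- **That the design is likely to fail its own target because of this slip.** If dropouts are independent at 20%, an arm of 17 keeps at least 14 with probability 0.55, and both arms do so with probability 0.30. But 18 per arm gives only 0.72 and 0.51. Much of the risk is chance variation in dropout, which dividing by 0.80 does not remove.

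**Conclusion.** The point holds as a small internal inconsistency. At 20% attrition, 17 per group leaves an expected 13.6 (27.2 in total), not the 14 (28) to which the 82% refers; meeting the allowance in full would take 18. This part is plain arithmetic on the plan's own figures and needs no assumption, and nothing elsewhere in the document corrects it.

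The size in power terms does rest on assumptions, namely the correlation and the number of measurements. Under the settings examined, it is about 1.3 points in expectation and about 3 points at 13 per arm. A reader might infer that the sample size is inadequate or that recruitment must rise; a difference of this size does not support either inference in a pilot.

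The unstated inputs matter more than the rounding. With the two listed time points and an assumed correlation of 0.5, interaction power at 14 per arm is already 72.1%. For the same reason, a revised power for 13 per group cannot be quoted reliably until those inputs are given.

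**What to change.** Keep 17 per group and change one sentence in the Power section, in one of two ways:

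- **Restate the allowance (simplest).** Say that 17 per group allows for up to 3 losses per arm, 3/17 = 17.6% attrition, while leaving the 14 needed for the stated power.
- **Keep 20% and restate the power.** Quote the power for 13 per group, the whole number left when 13.6 is rounded down, and state the within-person correlation and the number of measurements used.

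Neither option needs extra enrolment or changes the design or the analysis. The cost is a slightly less favourable attrition allowance or power figure. The second option also requires the sponsor to recover the inputs of the power calculation, which would be worth recording whichever option is taken.
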